7.2 Analysis Populations

The analysis populations are defined as follows:

- All Treated Patients: Includes all patients who received at least one dose of MT-401 or were randomized to SOC.
- All Randomized Patients: Includes all patients in Group 1 who were randomized with final dose and manufacturing process and are MRD⁻ prior to randomization by central testing and local testing, if a local test was also performed. A patient randomized based on negative MRD result per central test but confirmed to be MRD⁺ will be excluded from Group 1 analysis.

When MRD testing occurs with different methodology (eg, flow cytometry and PCR), the patient is considered MRD⁺ if either test detects MRD. If adjudication occurs between central testing and local testing for the same type of testing (eg, flow by central testing and flow by local testing), the final adjudicated result will be taken into account for the confirmed MRD result. A patient confirmed to be MRD⁺ prior to randomization will be excluded from Group 1 and will be included in Group 2 analysis if treated with MT-401.

- Per-Protocol (PP) Population: Includes all treated patients, as defined above, who have no major protocol deviations. If there is <5% difference in the all randomized patient population and the PP population for Group 1, no analyses will be performed on the PP population.

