If Cohort III data determines the 200×10^6 cell dose to be safe, the Phase 2 patients may be switched to receive the 200×10^6 cell dose, infused three times at intervals of at least 2 weeks.

In Cohorts IV and V, patients will receive three consecutive doses of MT-401, manufactured using the accelerated process, at a fixed dose of 100×10^6 cells and 200×10^6 cells, respectively, in fused at intervals of at least 2 weeks. The dose determined to be safe at the conclusion of Cohorts IV and V will determine the final Phase 2 dose.

Confidential Page 14 of 74

Statistical Methods

Analysis Populations:

All enrolled patients: All patients who sign the ICF and donor undergoes leuk apheresis..

All randomized patients in Phase 2 (Adjuvant - Group 1 only): All patients in Group 1 who are randomized with the final dose and manufacturing process and are MRD prior to randomization by central testing and local testing (if a local test was also performed). Efficacy analyses for Group 1 will be conducted in this population. A patient randomized based on negative MRD result per central test but confirmed to be MRD will be excluded from Group 1 analyses. The patient will be included in Group 2 Subgroup D analyses if treated with MT-401.

All treated patients: All patients who receive at least one dose of MT-401 or were randomized to SOC. Patients whose product includes fewer cells or does not meet specifications may still be treated, but will be summarized separately from patients whose product meets specifications. For Group 1 (adjuvant therapy), sa fety analyses will be conducted in this population, and sa fety data for patients randomized to SOC will also be shown for reference. For Group 2 (active disease), the primary and secondary efficacy analyses and safety analyses will be conducted in this population. For the Safety Lead-in (Cohorts I and II) and Cohorts III-V, all efficacy and safety analyses will be conducted in this population.

DLT-evaluable: All patients in the Safety Lead-in (Cohorts I and II) and Cohorts III-V who receive at least one dose of MT-401 and have had the opportunity to be followed for 28 days from the initial MT-401 infusion or have experienced a DLT.

Per-protocol in Phase 2: All treated patients, as defined above, who have no major protocol deviations. Select efficacy analyses for Group 1 and Group 2 will be conducted in this population for sensitivity analysis.

Planned Analysis:

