5.1. Patient Inclusion Criteria

All applicable inclusion and exclusion criteria must be met at Screening (up to 28 days before allogeneic HSCT for Group 1 patients, and prior to the start of manufacturing for Group 2 patients, or at the time of consideration for study) and at Baseline (re-assessment of eligibility within 14 days prior to group assignment for Group 1).

Patients are eligible to be included in the study only if all of the following criteria apply and the patient, in the judgement of the investigator, is an appropriate candidate for experimental therapy:

- 2. Eligible to receive donor-derived MT-401 following first allogeneic HSCT, are in ≤ third complete remission (CR3) prior to transplant (including matched sibling, matched unrelated donor with at least 6 of 8 HLA markers, or haploidentical with at least 5 of 10 HLA markers) as:
 - Adjuvant therapy for AML (**Group 1**) at 85-130 days post-HSCT defined as:
 - patients with CR_{MRD}- by central testing for purposes of randomization (if optional local MRD testing performed and results are positive, the patient will be moved to Group 2 subgroup D);
 - and are considered intermediate/high risk (e.g., pre-transplant MRD+, intermediate/adverse risk cytogenetics or received non-myeloablative or reduced intensity conditioning); or
 - Treatment for relapsed AML (first relapse post-HSCT) when disease occurs after transplant (Group 2) defined as
 - First relapse (MRD+ or frank relapse) post-HSCT
 - Patients in Group 1 who are randomized to Arm B (SoC) and experience first relapse (MRD⁺ or frank relapse) post-HSCT or experience relapse prior to randomization
 - Patients with frank relapse will enter into Subgroup C while patients with MRD⁺ disease will enter into Subgroup D
 - Safety Lead-in (Cohorts I and II) and Cohorts III-V defined as patients whose prior treatment course does not meet precise eligibility criteria but may still be approved upon review by the Sponsor as described above for Group 2 only

Note: Engraftment must be confirmed post-transplant (absolute neutrophil count $> 1000/\text{m}^3$ without granulocyte colony-stimulating factor for 7 days, donor chimerism $\ge 50\%$).

- 2. Are ≥18 years of age prior to administration of MT-401
- 3. Patients must have donor-derived cells available to make MT-401

Confidential Page 34 of 74

- 4. Karnofsky/Lansky score of ≥60
- 5. Life expectancy ≥ 12 weeks
- 6. Adequate blood, liver, and renal function

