9.2. Populations for Analyses

Populations for analyses are defined in Table 8.

Table 8. Populations for Analysis

Population	Description
All enrolled patients	All patients who sign the ICF and donor undergoes leukapheresis
All randomized patients in Phase 2 (Adjuvant - Group 1 only)	All patients in Group 1 who are randomized with final dose and manufacturing process, and are MRD prior to randomization by central testing and local testing (if a local test was a lso performed). Efficacy analyses for Group 1 will be conducted in this population. A patient randomized based on negative MRD result per central test but confirmed to be MRD will be excluded from Group 1 analyses. The patient will
All treated patients	be included in Group 2 Subgroup D analyses if treated with MT-401. All patients who receive at least one dose of MT-401 or were randomized to SoC. Patients whose product includes fewer cells or does not meet specifications may still be treated, but will be summarized separately from patients whose product meets specifications. For - Group 1, safety analyses will be conducted in this population, and safety data for patients randomized to SoC will also be shown for reference. For - Group 2, all efficacy analyses and safety analyses will be conducted in this population. For the Safety Lead-in (Cohorts I and II) and Cohorts III-V, all efficacy and safety analyses will be conducted in this population.
DLT-eva luable	All patients in the Safety Lead-in (Cohorts I and II) and Cohorts III-V who receive at least one dose of MT-401 and have had the opportunity to be followed for 28 days from the initial MT-401 infusion or have experienced a DLT.
Per-protocol in Phase 2	All treated patients, as defined above, who have no major protocol deviations. Select efficacy analyses for Group 1 and Group 2 will be conducted in this population for sensitivity analysis.

Confidential Page 51 of 74

Abbreviations: DLT=dose-limiting toxicity; ICF=informed consent form; MRD=minimal residual disease; SoC=standard of care

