For Group 1, randomization codes will be prepared to allow the clinical study sites to enroll patients by using an interactive response technology (IRT) system. Treatment group assignments will be known to site personnel (ie, investigator, pharmacist, and study staff) and patients. After completion of required screening procedures, patients will be assigned, using the randomization schedule, to MT-401 vs observation (SOC) with a 1:1 allocation. The randomization schedule will be created with stratification factors of pre-transplant MRD status (MRD⁺ vs. MRD⁻/Unknown) and cytogenetic risk (Unfavorable vs. Other) using random block sizes. SOC patients in Group 1-Arm B who relapse after randomization may cross over to Group 2 to receive MT-401, if the subgroup is open and/or Sponsor agreement.

For Group 2, after the patient's eligibility is established and informed consent has been obtained, the patient will be enrolled, and a number will be assigned through the IRT. Since this is a single-arm cohort, all enrolled patients who meet eligibility criteria will be treated with MT-401.

Due to the nature of the administration of MT-401 along with the fact that the endpoints are objectively evaluated without the concern for bias, the study is not blinded.

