- CR: For Subgroup C, CR is defined as the proportion of patients who achieve a best response of CR_{MRD-} or CR using the ELN recommendations. For Subgroup D, CR rate is defined as the proportion of treated patients who achieve a best response of CR_{MRD-}. Best overall response (BOR) is defined as the best response designation recorded between the date of first dose and the date of objectively documented relapse per ELN recommendations or the date of subsequent therapy, whichever occurs first. For patients without documented relapse or subsequent therapy, all available response designations will contribute to the BOR assessment.
 - The incidence of converting MRD+ to MRD- was chosen as the primary endpoint for Subgroup D based on the following rational: (1) 2017 ELN recommendations (Döhner et al, 2017) introduced a new response category of CR MRD- recognizing MRD assessment provides a more reliable predictor of outcome than morphological assessment and MRD status has been consistently shown to be an independent prognostic marker for disease outcome (Short et al, 2020; Schuurhuis et al, 2018). (2) Given the nature of single arm design, a binary endpoint was considered a more appropriate primary endpoint than a time to event endpoint such as RFS or OS.
- DOCR: For Subgroup C, DOCR is defined as the time between the date of first documented response of CR_{MRD-} or CR to the date of the first documented relapse per ELN recommendations or death due to any cause, whichever occurs first. For Group 2 Subgroup D, duration of complete response is defined as the time between the date of first documented response of CR_{MRD-} to the date of the first documented relapse per ELN recommendations or death due to any cause, whichever occurs first. For patients who neither relapse nor die prior to analysis cutoff or the start of new anti-cancer therapy, DOCR will be censored on the date of their last evaluable disease assessment on or after the assessment of first documented CR and prior to analysis cutoff or start of new therapy.

6.4.1.3 *Secondary Efficacy Variables*

Safety Lead-in (Cohorts I and II) and Cohorts III-V:

- CR (Active disease patients): defined as above for Group 2
- DOCR (Active disease patients): defined as above for Group 2

Phase 2 Adjuvant (Group 1):

- OS: defined as the time between the date of randomization and the date of death. A patient who has not died will be censored on their last contact date (“last known alive date”).

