7.4 Efficacy Evaluation

7.4.1 *Datasets Analyzed*

Efficacy analyses for Group 1 will be conducted in the all randomized patients population while efficacy analyses for Cohorts I-V and Group 2 will be conducted in the all treated patients population. Select efficacy analyses for Group 1 will be repeated in the PP population. A data listing of patients excluded from the PP Population, to include the reason for exclusion, will be presented.

7.4.2 *Demographic and Other Baseline Characteristics*

Demographic and baseline characteristics will include: age, sex, ethnicity, race, height, weight, and body mass index (BMI). Age will be calculated relative to date of informed consent, as follows:

- If the month and day portion of the informed consent date is prior to the month and day portion of the birthdate, age will be calculated as the year of informed consent minus the year of birth, minus one;
- If the month and day portion of the informed consent date is on or after the month and day portion of the birthdate, age will be calculated as the year of informed consent minus the year of birth.

BMI will be calculated as: weight (kg) / [height (cm) / 100]². Age, height, weight, and BMI will be summarized using descriptive statistics. Sex, age category (18-64 years, 65 years and above), ethnicity, and race will be summarized with the number and percentage of patients in each parameter category.

Disease history characteristics include: time since initial diagnosis (months), WHO classification, type of AML (secondary or treatment-related AML, de novo AML), disease status at screening, disease status at baseline, bone marrow blast percentage at baseline (for Cohort I-V and Group 2) complete remission prior to transplant (CR1/CR2/CR3; for Group 1 only), prior stem cell transplant (yes/no), time from transplant to randomization/first dose, time from first post-transplant relapse to first dose (for Cohort I-V and Group 2), history of post-transplant chronic GVHD (yes/no), maximum grade of chronic GVHD, history of post-transplant acute GVHD (yes/no), maximum grade of acute GVHD, type of transplant donor, conditioning regimen, MRD status pre- and post-transplant, genetic mutations identified, disease risk classification (favorable,

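### The 'All Randomized' set lets patients be removed after open-label randomisation for discordant baseline MRD, and those treated with MT-401 then count in the Subgroup D response rate

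*SAP*

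**What the plan says.** Central MRD results must be available before Group 1 randomisation (Protocol 6.3). SAP 7.2 defines All Randomized Patients as those randomised with the final dose and process who were MRD-negative before randomisation by central testing and, where done, local testing. It then drops any case of "A patient randomized based on negative MRD result per central test but confirmed to be MRD"-positive. Such a patient "will be excluded from Group 1 and will be included in Group 2 analysis if treated with MT-401". Protocol 9.2 (Table 8) and the synopsis name the destination: the patient will "be included in Group 2 Subgroup D analyses if treated with MT-401".

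The local test is not mandatory. Protocol 5.1 says that "if optional local MRD testing performed and results are positive, the patient will be moved to Group 2 subgroup D". Under SAP 7.2, when methods differ, one positive test makes the patient MRD-positive. When central and local results come from the same method, the adjudicated result is used if there was adjudication.

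This reduced set carries the primary comparison: "Efficacy analyses for Group 1 will be conducted in the all randomized patients population" (SAP 7.4.1). The trial is open-label: "Treatment group assignments will be known to site personnel" (SAP 6.3.2), and to patients.

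Subgroup D's primary endpoint is a best response of CR without MRD, counted from the date of first dose (SAP 6.4.1.2). SAP Table 2 grants that category on negativity by RT-qPCR or by flow cytometry. The protocol synopsis has MRD status monitored by central testing.

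**The concern.** There are two separate problems.

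**Group 1.** A patient can be randomised, have a known arm, and then be removed because a local result or an adjudication arrives later. A local positive known in time should already have kept the patient out of Group 1, so the rule matters for late results. Nothing says when confirmation must be finished, that it must be blind to arm, or that discordance must be looked for equally in both arms. None of the Group 1 analyses described restores these patients.

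**Subgroup D.** A removed patient's destination depends on treatment. A patient treated with MT-401 moves to Subgroup D. A removed SoC patient is in no efficacy set unless he or she crosses over and is treated. The moved patients were negative on the central test at baseline, and central testing is also how MRD is followed. Entry needs one positive test, whereas response can be met by one negative test. SAP 6.4.1.2 presents the endpoint as conversion from MRD-positive to MRD-negative, and these patients could meet it without converting.

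At stake are the intention-to-treat standing of the RFS comparison and the interpretation of a 30-patient response rate.

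**Working it through.** **Group 1: the plan's figure.** Inputs from SAP 7.6: 90 events, HR 0.55, two-sided alpha 0.05, 1:1 allocation. Schoenfeld power = Φ(√90/2 × |ln 0.55| − 1.96) = Φ(2.836 − 1.96) = 0.81. The stated 80% is reproduced.

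**Group 1: effect of removals on power.** If events were lost in proportion to patients removed from 150, the events are 90 × (150 − m)/150:

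| Removed (assumed) | Events | Power |
|---|---|---|
| 3 | 88.2 | 0.80 |
| 8 | 85.2 | 0.79 |
| 15 | 81.0 | 0.77 |

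The analysis is triggered at 90 events, so lost events would normally be made up. Power is not the issue; the exclusion is.

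**Subgroup D: chance that a moved patient counts as a responder.** Suppose post-baseline status follows the central test alone. The patient then responds if still relapse-free at the first post-dose assessment, Week 12 (2.76 months). With exponential RFS, the probability is 0.5^(2.76/median):

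- median 4 months (assumed, worse prognosis): 0.62
- median 8 months (plan, SoC): 0.79
- median 14.5 months (plan, 8 + 6.5): 0.88

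It approaches 1 if a central-negative Day 0 result dated on the day of first dose is counted.

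**Subgroup D: effect on the observed rate.** With k moved patients among 30 and a true rate of 30% in the rest (assumed), the expected rate is [0.30 × (30 − k) + p × k]/30:

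| k (assumed) | p = 0.62 | p = 0.79 | p = 0.88 |
|---|---|---|---|
| 3 | 33% | 35% | 36% |
| 5 | 35% | 38% | 40% |

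**Subgroup D: effect on the test.** SAP Table 3 uses a one-sided exact test at 0.05 with n = 30. For a 20% historical rate the critical count is 11/30: the tail is 0.026 at 20%, and power is 0.81 at 43% and 0.91 at 47%, which matches the table row. Now let 30 − k patients respond at 20% and k respond with probability p, and sum the two binomials. The chance of at least 11 responders becomes:

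| k (assumed) | p = 0.62 | p = 0.79 | p = 0.88 |
|---|---|---|---|
| 0 | 2.6% | 2.6% | 2.6% |
| 3 | 7.8% | 10.8% | 12.7% |
| 5 | 14.5% | 23.3% | 29.0% |

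SAP 7.4.7.5 instead states a two-sided 0.05 test. On that reading the critical count is 12/30, and the rate rises from 0.9% to 4.9% (k = 3) or 12.4% (k = 5) at p = 0.79.

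**The case against.** Much can be said for the rule. It concerns status before randomisation and applies to both arms. Removing patients who never met a baseline criterion is a recognised practice when it is done blind, on data fixed before assignment. MRD that first appears after randomisation is molecular relapse and stays an RFS event. Removed SoC patients also remain in the treated set for safety.

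Several stronger readings are tempting, and the documents do not support them:

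- **The rule favours MT-401 on RFS.** No direction can be derived from the text.
- **Only Arm A patients are moved.** The condition is treatment with MT-401, so a crossover patient from Arm B can also qualify.
- **Local testing clusters by site.** The plan says only that it is optional.
- **Moved patients respond almost automatically.** If the either-positive rule also governs post-baseline status, the originally positive method must turn negative. If adjudication overturned the central result, that result predicts little. The SAP does not say whether the rule applies after baseline.

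It is also fair that the illustrated shifts, 3 to 10 points, do not exceed the increase of more than 10-15% that SAP 7.6 calls meaningful, and that Table 3's interval around an observed 29% already runs from 14% to 48%.

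What stands is that the plan sets no deadline, no blinding, no analysis that keeps these patients, and no separation of them within Subgroup D. SAP 7.6 already separates patients who are CR without MRD after bridging and leaves them out of the 60.

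**Conclusion.** The concern holds as a gap in the rules; it does not show that bias will occur. The primary RFS set permits an exclusion after open-label assignment whose timing and blinding are uncontrolled. Its direction is unknown and its cost in power is slight. In Subgroup D, patients already central-negative may be counted as responders without any change in disease. Under the central-test-only reading and the assumed counts, a true 30% rate would appear as 33-40%. The one-sided false-positive rate against 20% would rise from 2.6% to between 8% and 29%. These sizes depend on three inputs the plan does not give: the number of moved patients, the true rate in the others, and how MRD is read after baseline. If few or no discordant patients arise, the effect is negligible. The change is still worth making because it costs little and is best made before arm-level results are seen.

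**What to change.** 1. **Primary RFS set.** Leave the restriction to the final dose and process as it is. Within it, keep every patient randomised on a negative central test, analysed in the assigned arm.
2. **RFS rule for discordant patients.** SAP Table 2 defines molecular relapse only after CR without MRD, so a retained patient with a discordant baseline has no clear event definition. State how relapse is determined for such patients, identically in both arms.
3. **Sensitivity analysis.** Move the MRD exclusion here, with adjudication done blind to arm and on the pre-randomisation sample only.
4. **Subgroup D.** Report moved patients separately, outside the 30 and outside the CR rate, as is already done for patients who are CR without MRD after bridging. State whether the either-positive rule applies after baseline.

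The cost is wording in the protocol synopsis, Protocol Table 8 and SAP 7.2, the RFS rule, and one sensitivity table. A few MRD-discordant patients remain in Group 1, which slightly dilutes the MRD-negative population.
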